4.4.4 Surgical Prophylaxis Population

The full analysis set defined according to the intention-to-treat (ITT) principle will include subjects who fulfill all of the following conditions:

- Received at least one infusion of the IMP.
- Entered the study with a confirmed congenital fibrinogen deficiency (second inclusion criterion).
- Presented with an episode of acute bleeding (third inclusion criterion).
- And plan to undergo a surgical procedure with a need for at least one infusion of the IMP (third inclusion criterion).

4.4.5 Subpopulations

Subpopulations based on the following categories will be examined:

- Severity of bleeding: minor versus major.
- Age: Paediatric (≤ 18 years) versus adult (18–64) versus elderly patients (≥ 65), if appropriate.
- Sex.

FORMA-02	JSS Medical Research - Data Management								 JSS <small>RESPONSIVE RELIABLE RESULTS</small>	
Statistical Analysis Plan										
Form Number: MNI-DM-BIS-01 v 6.0-T1	Current Version Number: 2.0			Previous Version Number: 1.1 9- April-2015				Date: 11-July-2016		

4.5 Flow Chart of Assessments

4.5.1 Flow Chart of Assessments for On-Demand Treatment of Acute Bleeding

Screening	Observations performed for each bleeding episode											Study Completion Visit					
	Day 1			All study days after Day 1 (at least 3 days for minor bleeding, 7 days for major bleeding)			Day of Last Infusion			24 hours (i.e., 1 day) after last infusion	Day 14 (± 2 days)	Day 30 (± 1 week)					
	Pre-infusion	Post-infusion		Daily	Pre-infusion [a]	1 h post-infusion [a] (± 15 min)	Pre-infusion	Post-infusion									
		1 h (± 15 min)	3 h (± 15 min)					1 h (± 15 min)	3 h (± 15 min)								
Eligibility and informed consent	x	#															
Demography	x																
Medical history, review of previous therapy	x	x															
Physical examination		x								x		x	x				
Vital signs	x	x	x			x		x	x	x							
Wells criteria for DVT and PE	x	x	x	x	x	x	x	x	x	x	x	x	x				
Height and weight	x																
Characterisation of bleeding episode	x																
Blood draw for:																	
Fibrinogen activity	x [b,c,d]	x [c,d]	x [d]	x [c,d]	x [b,c,d]	x [c,d]	x [b,c,d]	x [c,d]	x [d]	x [d]							
Fibrinogen antigen	x [b,d]	x [d]	x [d]	x [d]	x [b,d]	x [d]	x [b,d]	x [d]	x [d]	x [d]							
MCF [d]	x [b]	x					x										
Thrombogenicity [d]	x	x	x			x	x	x	x								
Immunogenicity [d]	x									x	x						
Safety lab (haematology and clinical chemistry) [c]	x	x	x	x [i]	x	x	x	x	x	x							
Retention plasma samples [e]	x [b]	x	x	x	x	x	x	x	x	x	x	x					
Retention serum samples [e]	x												x				
Urine or blood pregnancy test	x																
Infusion of Octafibrin		x [f]			x [f,g]		x										
Final haemostatic efficacy assessment										x							
AEs [h]		>	>	>	>	>	>	>	>	>	>	>	>				
Concomitant medications		>	>	>	>	>	>	>	>	>	>	>	>				

FORMA-02	JSS Medical Research - Data Management		 JSS <small>RESPONSIVE RELIABLE RESULTS</small>
Statistical Analysis Plan			
Form Number: MNI-DM-BIS-01 v 6.0-T1	Current Version Number: 2.0	Previous Version Number: 1.1 9- April-2015	Date: 11-July-2016

DVT = deep venous thrombosis; PE = pulmonary embolism; AE = adverse event; MCF = maximum clot firmness (clot strength).

To be re-reviewed if period between screening and treatment is more than 3 months.

- [a] If, based on the daily assessment, the investigator considers an additional infusion of *Octafibrin* necessary (see footnote f).
- [b] within 30 minutes before infusion
- [c] Measured in local laboratories.
- [d] Measured in the central laboratory.
- [e] Plasma retain sample for potential retesting; serum retain sample for potential viral testing.
- [f] If the *Octafibrin* infusion administered on this day is deemed the only infusion needed for treatment of the subject's bleeding event, the post-infusion assessments as detailed in the more comprehensive schedule for the Day of Last Infusion must be performed.
- [g] If the actual fibrinogen plasma level is below the accepted lower limit of the target fibrinogen plasma level, the subject **should** receive another infusion of *Octafibrin*. If the fibrinogen plasma level is greater than or equal to the accepted lower limit of the target fibrinogen plasma level, *Octafibrin* **should not** be administered.
- [h] Including completion of the Wells criteria for assessment of possible DVT and PE or any thromboembolic events or hypersensitivity reactions.
- [i] Haematology only

FORMA-02	JSS Medical Research - Data Management					 JSS RESPONSIVE RELIABLE RESULTS
Statistical Analysis Plan						
Form Number: MNI-DM-BIS-01 v 6.0-T1	Current Version Number: 2.0	Previous Version Number: 1.1 9- April-2015			Date: 11-July-2016	

To be re-reviewed if period between screening and treatment is more than 3 months.

[a] ≤ 30 minutes before and after each infusion of *Octafibrin*.

[b] Measured in local laboratories.

[c] Measured in central laboratory.

[d] Plasma retain sample for potential retesting; serum retain sample for potential viral testing.

[e] If the actual fibrinogen plasma level is below the accepted lower limit of the target fibrinogen plasma level, the subject **should** receive another infusion of *Octafibrin*.

If the fibrinogen level is greater than or equal to the accepted lower limit of the target fibrinogen level, *Octafibrin* **should not** be administered.

[f] Intraoperative efficacy assessment by surgeon.

[g] Postoperative efficacy assessment by haematologist.

[h] Including completion completion of the Wells criteria for assessment of possible DVT and PE or any thromboembolic events and hypersensitivity reactions.

FORMA-02	JSS Medical Research - Data Management		
Statistical Analysis Plan			
Form Number: MNI-DM-BIS-01 v 6.0-T1	Current Version Number: 2.0	Previous Version Number: 1.1 9-April-2015	Date: 11-July-2016

4.5.3 Schedule of Visits/Summary of Study Procedures

Refer to Section 6.1 of protocol – Observations performed throughout the study.

5 SEQUENCE OF PLANNED ANALYSES

An interim analysis will be performed after the data is available for the first bleeding episode of 10 subjects. Two of these subjects should be between 12 and 18 years old. Results will be included in the submission for registration. Descriptive efficacy and safety analysis will be performed and presented to IDMEAC.

6 GENERAL CONSIDERATIONS FOR STATISTICAL ANALYSIS

The descriptive statistics for continuous variables will be presented with number (n) of non-missing observations, mean, Standard Deviation (SD), median, minimum and maximum (or range). For categorical variables, descriptive statistics will be presented with number of eligible subjects and number (n) with percentage of observations in the various categories of the endpoint, where percentage will be based on the eligible subjects in the respective analysis set.

6.1 Study Population

6.1.1 Number of Subjects

A minimum of 24 subjects will be enrolled in the study to assess on-demand treatment of at least one bleeding episode. This will include at least 4 subjects aged between 12 and 18 years (only 18 and above in Russia). This will also include an assessment of at least 4 surgical procedures, 2 of which should be performed in subjects aged between 12 and 18 years (only 18 and above in Russia). The study will be conducted in approximately 15 centres worldwide.

6.1.2 Subpopulations

Subpopulations based on the following categories will be examined:

- Severity of bleeding: minor versus major.
- Age: Paediatric (<18 years) versus adult (18–64) versus elderly patients (≥65), if appropriate.
- Sex
- Race
- Surgical population

6.1.3 Sample Size Rationale

The number of subjects is limited by the very small number of subjects in this indication. Therefore no real sample size estimation is provided. Instead, the probabilities for different outcomes are provided, given a success rate of 95% for a total number of 24 subjects together with respective confidence intervals (CIs).

FORMA-02	JSS Medical Research - Data Management		
Statistical Analysis Plan			
Form Number: MNI-DM-BIS-01 v 6.0-T1	Current Version Number: 2.0	Previous Version Number: 1.1 9-April-2015	Date: 11-July-2016

6.2 Derived and Computed Variables

It is expected that variables will be derived and computed. The SAP will not be amended for additional variables that are not related to the primary or key secondary variables.

For analysis purpose the assessment made by the investigator on the 4-point rating scale will be transformed to a dichotomous endpoint with success as "Yes" defined as a rating of excellent or good and "No" as Moderate or Non or Missing). The success rate will be calculated as the proportion of patients with success.

Any additional derived variables will be identified and documented in the Statistical Analysis System (SAS®) programs that create analysis files.

The following variable will be calculated for the analysis tables: BMI

Variable Name	Description	Valid Values (Ranges)	Computation Methods, Notes, or Equation(s)
BMI	Body Mass Index	—	$BMI = \{\text{Weight (in Kg)} / (\text{Height (in meters)})^2\}$
Success	Overall clinical assessment of haemostatic efficacy	Yes/No	if value is 'excellent; or 'good', then Success = "Yes" if value is 'Moderate 'or 'None' or 'Missing', then Success = "No"

Body Mass Index (BMI) = $\{\text{Weight (in Kg)} / (\text{Height (in meters)})^2\}$

6.3 Handling of Drop-outs and Missing Values

In general, if not stated differently, missing data will not be imputed.

If the haemostatic efficacy assessment is missing it will be set to "none" in the ITT analysis. Subjects with missing haemostatic efficacy assessment will be excluded from the per-protocol PP population. LOCF (Last observation carried forward) approach will be used for body weight measurement for all analysis involving dose/kg BW.

Missing MCF and IVR values will not be replaced.

6.4 Analysis Software

All the Statistical Reports including Summary Tables, Listings and Graphs (TLGs) will be generated using a customized reporting SAS Version 9.3 for windows, SAS Institute, Cary, North Carolina, United States of America (USA).

FORMA-02	JSS Medical Research - Data Management		
Statistical Analysis Plan			
Form Number: MNI-DM-BIS-01 v 6.0-T1	Current Version Number: 2.0	Previous Version Number: 1.1 9-April-2015	Date: 11-July-2016

7 DEMOGRAPHICS AND BASELINE CHARACTERISTICS

The following information will be captured on enrolment:

Demographics: sex, age, weight and height (calculated body mass index), and ethnic origin.

Medical history: obtained by interviewing the subject/legal guardian and by performing a physical examination.

Previous and concomitant medication: obtained by interviewing the subject.

7.1 Demographics

Demographic variables will be summarized descriptively. Demographic variables will include age, weight, sex, height, BMI and ethnic origin. Variables that are measured on a continuous scale, such as the age of the subject at the time of enrollment, the number of non-missing observations (n), mean, median, SD, minimum, and maximum will be tabulated for Octafibrin. Variables that are measured on a categorical scale will be summarized using frequencies and percentages of Octafibrin.

7.2 Medical History

Medical history will be listed by body system coded by MedDRA version 17.1 or higher with Preferred Term.

8 EFFICACY ANALYSIS

8.1 Primary Efficacy Analysis

For bleeding efficacy, the primary endpoint is the overall clinical assessment of the haemostatic efficacy of Octafibrin in treating the first documented bleeding episode of each patient.

The first bleeding episode covers the time period from the first Octafibrin infusion until 24 hours (i.e., 1 day) after the last infusion or the end of the treatment observation period, whichever comes last. Frequency distribution will be provided for the haemostatic efficacy scale data. In addition, a 95% CI for the success rate in haemostatic efficacy (excellent or good) according to Casella (Blyth-Still-Casella interval) will be computed using StatXact® software.

For the following subjects the haemostatic efficacy outcome will be set to the worst category i.e., "none":

- Subjects who withdraw from the study due to lack of efficacy.
- Subjects receiving cryoprecipitate, or concentrates containing fibrinogen other than the IMP between first infusion and efficacy assessment (unless it is clearly documented that these products were administered for reasons unrelated to efficacy [e.g., pharmacy error]).
- Subjects with missing haemostatic efficacy assessment.

Haemostatic efficacy will be displayed by co variables (sex, age groups, race, weight and type of bleeding) in tables or with co variables in listings depending on the number per subgroup.

FORMA-02	JSS Medical Research - Data Management		
Statistical Analysis Plan			
Form Number: MNI-DM-BIS-01 v 6.0-T1	Current Version Number: 2.0	Previous Version Number: 1.1 9-April-2015	Date: 11-July-2016

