3.2 Overall Study Design and Plan

This is a multinational, multi-centre, prospective, open-label, uncontrolled, Phase III study to assess the efficacy and safety of *Octafibrin* for on-demand treatment of acute bleeding and surgical prophylaxis in subjects with congenital fibrinogen deficiency.

A total of 24 male and female subjects with congenital fibrinogen deficiency will be enrolled in the study. This will include at least 4 subjects aged between 12 and 18 years (only 18 and above in Russia). This will also include at least 4 surgeries, 2 of which should be performed in subjects aged between 12 and 18 years (only 18 and above in Russia). The study will be conducted in approximately 15 study centres worldwide.

During the study observation period, enrolled patients will be treated for any bleeding episodes or planned surgeries that can be managed under the protocol. Patients may remain in the study until the 24th patient has at least one documented bleeding episode. The study will be considered completed when a minimum of 24 subjects have at least one documented bleeding episode. The study as a whole should be completed within 5 years.

As many bleeding episodes or surgeries as possible occurring throughout the study observation period will be documented. Only the first bleeding episodes will be used for the analysis of the primary endpoint. All bleeding episodes documented in the study will be assessed as a secondary endpoint.

The investigator will inform the monitor of any recruitment difficulty or delay of the anticipated completion date.

Patients should be treated with the investigational medicinal product (IMP) whenever possible. If, in the opinion of the investigator, a bleeding episode is not effectively stopped or surgical prophylaxis is not adequate after the recommended dose of *Octafibrin* has been administered, the subject may receive a different licensed fibrinogen concentrate (e.g., Haemocomplettan P®/RiaSTAPTM) or whatever the investigator considers standard of care. The use of another licensed fibrinogen concentrate is also permitted in emergency situations, e.g., if the IMP is not available for the patient in time.

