4.3 Exclusion Criteria

Subjects who meet any of the following criteria are not eligible for the study:

- 1. Life expectancy <6 months.
- 2. Bleeding disorder other than congenital fibrinogen deficiency, including dysfibrinogenaemia.
- 3. Prophylactic treatment with a fibrinogen concentrate.
- 4. Treatment with:
 - Any fibrinogen concentrate or other fibrinogen-containing blood product within
 2 weeks prior to start of treatment for the bleeding episode or surgery
 - Any coagulation-active drug (i.e., non-steroidal anti-inflammatory drugs, warfarin, coumarin derivatives, platelet aggregation inhibitors) within 1 week prior to start of treatment for the bleeding episode or surgery, or as a planned or expected medication during the time period from Day 1 until 24 hours (i.e., 1 day) after the last *Octafibrin* infusion.

- 5. Presence or history of:
 - Hypersensitivity to study medication
 - Deep vein thrombosis or pulmonary embolism within 1 year prior to start of treatment for the bleeding episode or surgery
 - Arterial thrombosis within 1 year prior to start of treatment for the bleeding episode or surgery
 - Hypersensitivity to human plasma proteins
 - Oesophageal varicose bleeding
 - End-stage liver disease (i.e., Child-Pugh score B or C).
- 6. Pregnant women within the first 20 weeks of gestation.
- 7. Currently breast-feeding.
- 8. Known positive HIV infection with a viral load >200 particles/μL or >400,000 copies/mL.
- 9. Polytrauma 1 year prior to start of treatment for the bleeding episode or surgery.
- 10. Diagnosis or suspicion of a neutralising anti-fibrinogen inhibitor currently or at any time in the past.
- 11. Acute or chronic medical condition which may, in the opinion of investigator, affect the conduct of the study, including
 - Subjects receiving immune-modulating drugs (other than anti-retroviral chemotherapy) such as alpha-interferon, prednisone (equivalent to >10 mg/day), or similar drugs at study start
 - Subjects having evidence or a history (within the previous 12 months) of abuse of any drug licit or illicit substance.
- 12. Participation in another interventional clinical study currently or during the past 4 weeks.

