7.2 Efficacy Assessments

7.2.1 Assessments for Primary Efficacy Endpoint

The primary endpoint is the overall clinical assessment of the haemostatic efficacy of *Octafibrin* in treating the first documented bleeding episode of each patient.

- The **first bleeding episode** covers the time period from the first *Octafibrin* infusion until 24 hours (i.e., 1 day) after the last infusion or the end of the treatment observation period, whichever comes last.
- The **investigator's overall clinical assessment** covers the entire time period of the first bleeding episode as defined above. The assessment includes the clinical condition of the subject, laboratory values such as haematocrit and haemoglobin, as well as any additional haemostatic treatments.

The investigator's overall clinical assessment of haemostatic efficacy will be based on a 4-point haemostatic efficacy scale (Table 2). The final efficacy assessment of each patient will be adjudicated by the IDMEAC.

Table 2: Overall clinical assessment of haemostatic efficacy

Category	Definition
Excellent	Immediate and complete cessation of bleeding in the absence of other haemostatic intervention as clinically assessed by the treating physician; and/or <10% drop in haemoglobin compared to pre-infusion.
Good	Eventual complete cessation of bleeding in the absence of other haemostatic intervention as clinically assessed by the treating physician; and/or <20% drop in haemoglobin compared to pre-infusion.
Moderate	Incomplete cessation of bleeding and additional haemostatic intervention required, as clinically assessed by the treating physician; and/or between 20 and 25% drop in haemoglobin compared to pre-infusion.
None	No cessation of bleeding and alternative haemostatic intervention required, as clinically assessed by the treating physician; and/or >25% drop in haemoglobin compared to pre-infusion.

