9.4 Efficacy Analysis Plan

9.4.1 Primary Endpoint

The primary endpoint is the overall clinical assessment of haemostatic efficacy of *Octafibrin* in treating the first documented bleeding episode of each patient. The first bleeding episode covers the time period from the first *Octafibrin* infusion until 24 hours (i.e., 1 day) after the last infusion or the end of the treatment observation period, whichever comes last (see Section 3.1.1).

Frequency distribution will be provided for the haemostatic efficacy scale data. In addition, a 90% CI for the success rate in haemostatic efficacy (excellent or good) according to Casella (Blyth-Still-Casella interval [28]) will be computed using SAS software [29].

For the following subjects, the haemostatic efficacy outcome will be set to the worst efficacy category, i.e., 'none':

- Subjects who withdraw from the study due to lack of efficacy.
- Subjects receiving cryoprecipitate or concentrates containing fibrinogen other than the IMP between first infusion and efficacy assessment (unless it is clearly documented that these products were administered for reasons unrelated to IMP efficacy [e.g., pharmacy error]).
- Subjects with missing haemostatic efficacy assessment.

Haemostatic efficacy will be displayed by covariables (sex, age groups, weight, type of bleeding) in tables or with covariables in listings depending on the number per subgroup.

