3.2 Study Endpoints

3.2.1 Primary Endpoint

The primary endpoint is:

- The primary endpoint is the overall clinical assessment of haemostatic efficacy of Octafibrin in treating the first documented bleeding episode of each patient. The first bleeding episode covers the time period from the first Octafibrin infusion until 24 hours (i.e., 1 day) after the last infusion or the end of the treatment observation period, whichever comes last.

The investigator's overall clinical assessment of haemostatic efficacy for bleeding will be based on a 4-point haemostatic efficacy scale (see table below). The final efficacy assessment of each patient will be adjudicated by the Independent Data Monitoring & Endpoint Adjudication Committee (IDMEAC). The number of subjects per outcome category will be assessed in the final analysis.

Category	Definition
Excellent	Immediate and complete cessation of bleeding in the absence of other haemostatic intervention as clinically assessed by the treating physician; and/or <10% drop in haemoglobin compared to pre-infusion.
Good	Eventual complete cessation of bleeding in the absence of other haemostatic intervention as clinically assessed by the treating physician; and/or <20% drop in haemoglobin compared to pre-infusion.
Moderate	Incomplete cessation of bleeding and additional haemostatic intervention required, as clinically assessed by the treating physician; and/or between 20 and 25% drop in haemoglobin compared to pre- infusion.
None	No cessation of bleeding and alternative haemostatic intervention required, as clinically assessed by the treating physician; and/or >25% drop in haemoglobin compared to pre-infusion.

FORMA-02	JSS Medical Research - Data Management		
Statistical Analysis Plan			
Form Number: MNI-DM-BIS-01 v 6.0-T1	Current Version Number: 2.0	Previous Version Number: 1.1 9-April-2015	Date:11-July-2016

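### The rule that sets rescued bleeds to 'none' names only cryoprecipitate and other fibrinogen concentrates, and the scale's 'and/or' lets a bleed rescued with another agent count as a success

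*SAP*

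**What the plan says.** **Override.** SAP 8.1 sets the haemostatic outcome to 'none' in three situations: withdrawal for lack of efficacy, a missing assessment, and "Subjects receiving cryoprecipitate, or concentrates containing fibrinogen other than the IMP between first infusion and efficacy assessment". The third does not apply when the product was clearly given for reasons unrelated to efficacy. Protocol 9.4.1 has the same product list: "Subjects receiving cryoprecipitate or concentrates containing fibrinogen other than the IMP between first infusion and efficacy assessment".

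**Permitted rescue.** If a bleed is not controlled after the recommended dose, Protocol 3.2 allows another licensed fibrinogen concentrate "or whatever the investigator considers standard of care". Protocol 4.4.1 and 4.8 repeat this.

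**Scale** (SAP 3.2.1; Protocol 7.2.1, Table 2). Each category has a clinical limb and a haemoglobin limb, joined by 'and/or'. Excellent reads "Immediate and complete cessation of bleeding in the absence of other haemostatic intervention as clinically assessed by the treating physician; and/or <10% drop in haemoglobin". Good has a clinical limb with the same no-other-intervention condition, then "and/or <20% drop in haemoglobin compared to pre-infusion". The clinical limb of Moderate begins "Incomplete cessation of bleeding and additional haemostatic intervention required". Success means Excellent or Good (SAP 6.2 and 8.2).

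**Safeguards.** Protocol 7.2.1 requires the investigator's assessment to include "laboratory values such as haematocrit and haemoglobin, as well as any additional haemostatic treatments". The final assessment is adjudicated by the IDMEAC.

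**The concern.** The list of products that force a failure is shorter than the list of products an investigator may use when Octafibrin has not worked. Plasma, antifibrinolytics and local haemostatics could all come under standard of care, and none is in the override. For those products the classification rests on the scale alone.

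The scale would exclude such bleeds from success if the no-other-intervention condition were mandatory. It is not. The condition sits in one limb, and the haemoglobin limb, which can stand alone under 'and/or', has no such condition.

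At stake is the meaning of the primary success rate. Through this route a failure can become a success, never the reverse. The trial is open-label and single-arm and is tested against a fixed threshold, so no control group absorbs the shift.

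**Working it through.** **1. A rescued bleed traced through the text.** Take a first bleed that Octafibrin does not control. The investigator gives plasma or an antifibrinolytic, the bleeding stops, haemoglobin has fallen by less than 20%, and the rating is recorded.

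| Rule | Applies? |
|---|---|
| Override (SAP 8.1) | No: the product is neither cryoprecipitate nor a fibrinogen concentrate, the subject has not withdrawn, and the rating is not missing |
| Excellent or Good, clinical limb | No: another haemostatic intervention was used |
| Good, haemoglobin limb | Yes: fall below 20% (Excellent if below 10%) |
| Moderate, clinical limb | Yes if cessation means cessation on Octafibrin; no if it means the state after rescue |
| None, clinical limb | Yes if Octafibrin had no effect and cessation means cessation on Octafibrin; otherwise no |
| Moderate or None, haemoglobin limb | No: these need a fall of 20% or more |

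On either reading of cessation, Good is satisfied literally. On the reading most favourable to the plan, Good and a failure category are both satisfied, and the text does not say which prevails.

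**2. The plan's own figures.** Inputs from SAP 8.2: N = 24, threshold 0.6, two-sided 95% Blyth-Still-Casella interval, assumed true rate 0.95. With X ~ Binomial(24, 0.95), P(X ≥ 19, 20, 21, 22) = 0.9990, 0.9940, 0.9702, 0.8841. SAP Table 1 states 0.999, 0.994, 0.970, 0.884. The recomputed lower limits are 0.594 at 19/24 and 0.633 at 20/24, also as stated. The decision rule is therefore at least 20 successes in 24. Its exact type I error at p = 0.60 is P(X ≥ 20) = 0.0134, against a nominal one-sided 0.025.

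**3. Effect of misclassification.** Let m be the share of true failures scored as success by this route. The documents give no rescue rate, so m is an assumption. The apparent success rate is p + (1 − p)m, which at p = 0.60 is 0.60 + 0.40m.

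| m (assumed) | Apparent rate | P(X ≥ 20 of 24) |
|---|---|---|
| 0 | 0.60 | 0.0134 |
| 0.05 | 0.62 | 0.0217 |
| 0.10 | 0.64 | 0.0340 |
| 0.20 | 0.68 | 0.0770 |

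**4. Effect of a single bleed.** One subject is 1/24 = 4.2 percentage points. Moving from 20/24 to 19/24 takes the lower limit from 0.633 to 0.594, across 0.6. At the SAP's assumed rate of 0.95, the probability of landing on exactly 20 is 0.9940 − 0.9702 = 0.0238, or about 2.4%.

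**The case against.** The strongest reply is that the scale already deals with rescue. The endpoint is the efficacy of Octafibrin, so incomplete cessation with another intervention required naturally describes a bleed that Octafibrin did not control. Such a bleed is Moderate, or None if there was no effect, and both are failures. This is the more sensible reading of those limbs. A reader might infer that a rescued bleed fits no clinical category at all, but that holds only if cessation is read as the state after rescue, and the documents do not require that reading. What remains is the 'and/or': even on the sensible reading the haemoglobin limb still supports Good.

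Second, a false success would need both the investigator and the committee to discount a recorded rescue. That is a real safeguard, but partial. No supplied text says how additional treatments count, and SAP 6.2 and 8.2 describe the dichotomy in terms of the investigator's rating. The IDMEAC charter and Protocol version 7.0, which the SAP cites, were not supplied and may contain a rule.

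Third, a reader might see a contradiction between the override and exclusion criterion 4, which covers "Any fibrinogen concentrate or other fibrinogen-containing blood product" (the per-protocol criterion in SAP 4.4.3 is similar). Those criteria concern the two weeks before treatment, whereas the override concerns products given after the first infusion. The comparison shows that a wider wording was available; it does not show an inconsistency.

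**Conclusion.** The gap is real. The override covers fewer products than permitted rescue, and 'and/or' makes optional the one scale condition that would cover the rest. As written, a bleed stopped with plasma or another haemostatic agent, with a haemoglobin fall below 20%, can be counted as a success.

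The size is uncertain. The inflation figures rest wholly on assumed misclassification shares. At 5% the false-positive probability (2.2%) is still below the nominal 2.5%; at 10% (3.4%) and 20% (7.7%) it is above. A reader might infer that any one such bleed would reverse the trial's conclusion. That is true only at exactly 20/24, an outcome with about 2.4% probability if the SAP's 95% rate is right. Nor do the documents show that rescued bleeds will be scored as successes, only that no supplied rule prevents it. The direction of bias is clear and the remedy is cheap, so the rule should be closed.

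**What to change.** In SAP 8.1, with matching wording in Protocol 9.4.1, the scale in Protocol 7.2.1 and the IDMEAC charter:

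- Extend the second override item to any fibrinogen-containing product other than the IMP (concentrate, cryoprecipitate or plasma) given between first infusion and efficacy assessment. Keep the exemption for use clearly documented as unrelated to IMP efficacy.
- Add that any bleed for which another haemostatic intervention was given because of insufficient IMP effect counts as non-success, rated no better than Moderate, whatever the haemoglobin fall.

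If the charter or Protocol version 7.0 already holds such a rule, state or cite it in the SAP.

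This changes outcome classification only; which rescue treatments are permitted stays as it is. The data exist already, because Protocol 4.4.1 requires concomitant therapies to be recorded in the CRF. The costs are a possibly slightly lower observed success rate and a small alignment of protocol and charter, so it is not purely a SAP edit.
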